# Actual test sequence:

- a) Screening phase: In which the examiner will initially determine by single letter presentations what would be the smallest Snellen chart (or equivalent) level at which the subject will correctly identify letters.
- b) Testing phase: the examiner will start presenting letters of the size determined at the screening phase and smaller ones.
- c) Test continuation: if a letter is missed at a level, one level larger will be added to the testing. If a letter is correct at a level, one level smaller will be added to the mix.
- d) Acuity determination: Tests of 5 letters at each level until smallest level with 5/5 letters correct and the smallest level with 0/5 correct are determined.
- e) Quad view: at any time during a refraction, the ECP may provide a patient with a "quad view". This mode shows four different prescriptions simultaneously and allows the patient to switch from a memory-based decision to a solely vision-based decision.

#### 4.6 Letter scores calculation

With the lens correction obtained and present either on the phoropter or the LFR-260, the subject will be asked to read the Snellen chart (or equivalent) emphasizing that each letter will be scored and will ask the subject to take their time in answering in order to achieve best identification. The examiner will record each letter identified correctly on a score sheet. If a letter is not correctly recognized it will not be recorded, each correct letter is a point. The score of each line, even if zero, and the total score for the eye will be recorded right after the examination and recorded in the patient chart and the case report form.

# 4.7 Subject Screening and Recruitment

A study coordinator (e.g. research nurse or staff member) designated specifically for this study, investigator, or sub-investigator at each investigative site will approach each potential subject and inquire about their interest and eligibility in participating in this study. If the patient wishes to participate, a member of the research team will go through the informed consent / assent (where applicable) process, which will explain the purpose of the study, the procedures, the risk/benefits, alternatives to participation, and their confidentiality. After the consent process, the subject will be screened to confirm eligibility.

At the baseline visit, each subject choosing to participate will sign and date an informed consent and HIPAA authorization / assent (where applicable). A copy of the consent and authorization will be placed into the subject's medical record.

Study guidelines, aimed at helping guide the subject in their follow-up responsibilities, will include a subject information worksheet and site contact information for advice in case of complications or questions regarding follow-up visits.

#### 4.8 Randomization

The randomization will be performed between the LFR-260 and the traditional phoropter within site to account for the first system used. Randomization will be carried out according to the blocks procedure to avoid order imbalance of first device used in the trial.

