# 2.5 Hypotheses

# 2.5.1 Primary Effectiveness Hypothesis

The primary hypothesis for this study is that the probability of simultaneously achieving good clinical agreement for sphere, cylinder, and axis exceeds a performance goal (PG) for measurements made by the LFR-260 compared to those obtained using traditional phoropter. The *a priori* PG is 0.80. Good clinical agreement is defined as a sphere and cylinder measurements that are within +/- 0.5 D and within 10 degrees for axis among subjects with low astigmatism and within 5 degrees among subjects with moderate to high astigmatism.

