# 7.0 Statistical Analysis

# 7.1 Study Design and Randomization

The LFR-260-101 study is a multi-center, open-label, 2x2 cross-over design with the aim of investigating the effectiveness of the LFR-260 phoropter device compared to the traditional phoropter.

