# 7.4 Primary Effectiveness Hypothesis

The primary hypothesis for this study is that the probability of simultaneously achieving good clinical agreement for sphere, cylinder, and axis exceeds a performance goal for measurements made by the LFR-260 compared to those obtained using the control device, *traditional phoropter*.

Symbolically, the null and alternative effectiveness hypotheses are: :

Ho:  $\pi \le PG$ Ha:  $\pi > PG$ 

Where  $\pi$  is the true probability that the LFR 260 is within 0.5D (+/-) in measuring sphere and cylinder results and within 10 degrees for axis results among subjects with low astigmatism and within 5 degrees among subjects with moderate to high astigmatism from the traditional phoropter.

For this study, PG is set to 0.80.

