# 7.5 Sample Size Determination

If the true  $\pi$  is equal to 0.90, then, a 1-sided exact binomial test at alpha=0.05 with 216 eyes (108 subjects) has 99% power.

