# 7.6 Testing of Primary Effectiveness Hypothesis

The lower bound (LB) of a 1-sided exact binomial confidence interval will be determined and compared to 0.80. If LB exceeds 0.80, the device will have met the a priori defined performance goal.

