# 7.7 Other Planned Analyses

#### 7.7.1 Bland-Altman Agreement Analysis

Supporting analyses will evaluate the distribution of paired differences between LFR-260 and reference for the three dimensions (sphere, cylinder, and axis) using Bland-Altman agreement analysis. This will include determination of the standard deviation of paired differences, the 95% limits of agreement, and an evaluation of systematic bias. The Bland-Altman plot of paired differences versus the mean of measurements will be provided. The relationship between bias and the mean of measurements will characterized. The same analysis will be applied to the vector difference between LFR-260 measurements and the gold standard in terms of sphere and cylinder measurements. The vector differences is square root of (X1-Y1) + (X2-Y2) where the X1 and X2 are measurements of sphere and cylinder using the investigational devices and Y1 and Y2 are the same measurements using the gold standard.

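### Device order is block-randomised but no agreement analysis uses it, so any order effect would widen the Bland-Altman limits in Section 7.7.1

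*Combined protocol and SAP*

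**What the plan says.** Section 7.1 describes a "multi-center, open-label, 2x2 cross-over design". Section 4.8 randomises the first device "within site to account for the first system used" and gives the reason for blocking: "Randomization will be carried out according to the blocks procedure to avoid order imbalance of first device used in the trial". Under Section 4.9.1 both devices are used at the same visit, one after the other.

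The agreement analyses are these:

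- **Section 7.6 (primary):** "The lower bound (LB) of a 1-sided exact binomial confidence interval will be determined and compared to 0.80". This is one proportion over all eyes.
- **Section 7.7.1 (Bland-Altman, supporting):** "This will include determination of the standard deviation of paired differences, the 95% limits of agreement, and an evaluation of systematic bias". The paired differences are treated as one set.
- **Section 7.7.2 (homogeneity):** by site, gender, age category, race and ethnicity.
- **Section 7.7.3 (imputation):** the model names the measurements from both devices, age and gender.
- **Section 7.7.4 (reliability):** intraclass correlations.

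None has a period or sequence term or a summary by order, and the statistical part of the synopsis adds none. Order enters Section 7 only through the analysis sets. ITT follows the randomised group, which under Section 3.3 is the order. FAS follows the order actually used and carries the primary safety analyses.

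**The concern.** Randomising the order balances an order effect in the average difference between devices. Limits of agreement describe spread, and balance does not protect spread. If readings shift between the first and second refraction, the pooled limits contain that shift as well as device disagreement, and nothing in the planned output lets a reader tell the two apart.

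A shift is plausible, though the documents do not show one. No interval between the two devices is stated. Testing is without cycloplegia, and Sections 3.2 and 4.4 both treat instrument myopia as something to control. In the reproducibility subset (Section 4.9.2), subjects who start with the LFR-260 have two refractions on it before the phoropter, so prior exposure differs by order.

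**Working it through.** **Inputs from the documents.** 108 subjects, 216 eyes, one-sided alpha 0.05 and assumed true rate 0.90 (Section 7.5); goal 0.80 (Section 7.4); margin 0.5 D for sphere and cylinder (Section 2.5.1).

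**Inputs assumed.** Neither the SD of paired differences nor an order effect is given. I take a within-order SD of 0.25 to 0.35 D for sphere and shifts of 0.05, 0.125 and 0.25 D. No allocation ratio is given; I take 1:1, so 54 subjects per order.

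**The plan's own figure.** Section 7.5 states that if the true rate "is equal to 0.90, then, a 1-sided exact binomial test at alpha=0.05 with 216 eyes (108 subjects) has 99% power". The smallest count r with P(X ≥ r | 0.80) ≤ 0.05 is 183 of 216 (84.7%). Attained alpha is 0.0461 and power at 0.90 is 0.9946. The 99% reproduces, and the point below does not alter it.

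**Effect of order on the paired difference.** Let b be the device bias (LFR-260 minus phoropter) and p the shift from first to second refraction.

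- LFR-260 first: mean difference = b − p.
- Phoropter first: mean difference = b + p.
- Average of the two = b, so the mean is protected.
- Pooled variance = SD² + p², so the pooled limits are b ± 1.96 × sqrt(SD² + p²), and the widening factor is sqrt(1 + (p/SD)²).

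Half-width of the limits in D, with the widening in brackets:

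| SD | p = 0 | p = 0.05 | p = 0.125 | p = 0.25 |
|---|---|---|---|---|
| 0.25 | 0.490 | 0.500 (2.0%) | 0.548 (11.8%) | 0.693 (41.4%) |
| 0.30 | 0.588 | 0.596 (1.4%) | 0.637 (8.3%) | 0.765 (30.2%) |
| 0.35 | 0.686 | 0.693 (1.0%) | 0.728 (6.2%) | 0.843 (22.9%) |

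A simulation of 200,000 differences (within-order SD 0.304 D, b = 0.05 D, p = 0.25 D) gave a mean of 0.049 D whether pooled or averaged over orders. The pooled SD was 0.392 D and the within-order SD 0.303 D.

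**Can the order effect be estimated?** It is half the difference between the two order-specific means. With 108 eyes per order and SD 0.30 D, its standard error is 0.5 × sqrt(2 × 0.09 × deff / 108), where deff allows for two eyes per subject. That is 0.020 D at deff 1 and 0.025 D at deff 1.5, so the 95% interval is about ±0.04 to ±0.05 D. A shift of 0.125 D would be visible.

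**Would agreement proportions by order show it?** Not if b = 0. Shifts of −p and +p leave the same share within 0.5 D: at SD 0.30 D, 87.6% in both orders for p = 0.125 D and 79.1% in both for p = 0.25 D. The order-specific means are needed.

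**The case against.** The case for leaving the plan alone is substantial. Bland-Altman is expressly supporting. Blocked order already protects the mean bias against a period effect. A pure period effect widens the limits and lowers agreement, so it works against the device and opens no route to false success. Fogging and the age mix already address instrument myopia. The size of any shift is unknown, and one of 0.05 D hardly matters. All of this stands. It limits the importance of the point but does not make the pooled limits a clean measure of device disagreement.

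A reader might infer more than the documents support:

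- **That order effects would push the device below the goal.** At p = 0.25 D the share within 0.5 D is 79.1% if the SD is 0.30 D but 84.0% if it is 0.25 D, so the result follows from the assumed SD. It is also a share for sphere alone, whereas "For this study, PG is set to 0.80" refers to sphere, cylinder and axis together.
- **That carry-over from the LFR-260 hides a device shift.** Nothing in the documents shows this. If a carry-over c entered a following phoropter reading, the order means would be b − p − c and b + p. Their average is b − c/2 and half their difference is p + c/2. The design cannot separate p from c.
- **That the statistical section ignores order altogether.** The ITT and FAS definitions refer to it. The gap is confined to the agreement analyses.

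**Conclusion.** The point holds in a limited form. Order is randomised and then not used in any agreement analysis, so a shift between first and second refraction would inflate the SD and limits in Section 7.7.1. With an assumed sphere SD of 0.25 to 0.35 D and 1:1 order, the widening runs from 2% or less at 0.05 D to about 23 to 41% at 0.25 D. The mechanism is a matter of algebra; the size rests wholly on these assumptions. The primary test and its stated power do not need to change. This is a minor improvement to a supporting analysis.

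**What to change.** In Section 7.7.1:

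1. Report the mean paired difference by device order for sphere, cylinder and axis.
2. Estimate bias as the average of the two order-specific means, and the order effect as half their difference. Use standard errors that allow for two eyes per subject.
3. Give limits of agreement from the within-order SD of the paired differences, beside the pooled limits.
4. Show the agreement proportion by order as a descriptive table. Note that equal proportions do not rule out a period effect, and that the order contrast cannot separate period from carry-over.

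Work from the paired differences. A crossover mixed model on the raw readings with subject as the only random effect would put fellow-eye differences into the residual. With a paired-difference SD of 0.30 D (error variance 0.045 per reading) and an assumed eye-within-subject SD s, the residual variance is about (2s² + 3 × 0.045)/3. The limits, 1.96 × sqrt(2 × residual variance), are then about ±0.74 D for s = 0.20 D and ±0.99 D for s = 0.35 D, against a true ±0.59 D.

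Leave the decision rule in Section 7.6 unchanged. The cost is a few lines of analysis-plan wording. Device order is already fixed at randomisation, and no extra subjects, visits or measurements are needed.

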# 4.9 Visit Summary

# 4.9.1 Screening/Initial Assessment

The procedures to be completed at Visit 1 are as follows:

- Screening: Talk to the patient to determine if he/she would fit study requirements, and assess likelihood of meeting enrollment criteria.
- Informed Consent / Assent: Obtain subject informed consent or assent for minors. Allow subject or their legally authorized representative (LAR) sufficient time to thoroughly read and understand the consent form and answer any questions he/she may have about the study. If subject provides informed consent, complete the subject enrollment log.
- Inclusion Criteria: Ensure subject meets all inclusion criteria.
- Exclusion Criteria: Ensure subject does not meet any of the exclusion criteria.
- Pre-study assessments: Obtain medical history and demographics from subject.
- Prior medications/therapy: Note any medications or therapy that the subject is currently taking. Medications of note include:

- Randomization: determine the order of system utilized for testing
- Device #1 testing including:
  - o Baseline Visual Acuity

- o Refraction (including retinoscopy)
- Measure Best Corrected Visual Acuity
- Device #2 testing including:
  - o Baseline Visual Acuity
  - o Refraction (including retinoscopy)
  - Measure Best Corrected Visual Acuity
- Patient satisfaction with LFR-260 device Quad view
- Eyecare provider satisfaction with LFR-260 related to usability, convenience

\*Conclusion of Study: Study coordinator will complete the Study Exit Form, which will indicate the conclusion of subject participation in this study.

\*For subjects included in the Precision Tests or Remote Testing (4.9.2 and 4.9.3), Study Exit Form to be completed after all testing is completed.

#### 4.9.2 Precision Tests

# 1. Repeatability Testing (+1 hour post initial testing)

In a subset of 33 patients (11 per location), LFR-260 testing will be repeated by the same ECP to confirm the initial findings. One ECP per location will perform Repeatability Testing for a total of 3 ECPs included for this testing method.

- ECP will complete Refraction with LFR-260 one hour post initial testing
- Measure Best Corrected Visual Acuity
- Conclusion of Study: Study coordinator will complete the Study Exit Form, which will indicate the conclusion of subject participation in this study.

# 2. Reproducibility Testing

In a separate subset of 33 patients (11 per location), LFR-260 testing will be reproduced by two separate ECP operators at each location for a total of 6 ECPs.

If the patient is randomized to Group I, the steps listed below will be completed at the beginning of the patient visit. If the patient is randomized to Group II, the steps listed below will be completed after the eye exam with use of the traditional phoropter.

- 1. ECP #1 will complete Refraction with LFR-260.
  - a. Best Corrected Visual Acuity will be measured.
- 2. ECP #1 will leave the room, and ECP #2 will complete Refraction with LFR-260.
  - a. Best Corrected Visual Acuity will be measured.

3. Conclusion of Study: Study coordinator will complete the Study Exit Form, which will indicate the conclusion of subject participation in this study.

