# 7.7.4 Reliability and Repeatability Analysis

Reliability of LFR-260 will be conducted in a subset of subjects for which measurements will be obtained twice in an office context. This analysis will be repeated in a remote context. Reliability will be evaluated using intraclass correlations for each of the continuous measurements, sphere, cylinder, and axis and for the vector measurement of sphere and cylinder.

For a subset of 33 subjects (66 eyes), the LFR-260 device will be measured again approximately 60 minutes after the initial assessment in order to measure the repeatability/accuracy of the device.

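### The reproducibility subset does not counterbalance which ECP refracts first and states no interval between readings, so the protocol does not ensure that operator, order and time effects can be separated

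*Combined protocol and SAP*

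**What the plan says.** Section 4.9.2 defines two precision subsets of 33 different subjects each, 11 per location.

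- **Repeatability.** "LFR-260 testing will be repeated by the same ECP to confirm the initial findings". The timing is "ECP will complete Refraction with LFR-260 one hour post initial testing", and the study flowchart gives a window of 30 minutes either side of one hour in the repeatability column only. On operators: "One ECP per location will perform Repeatability Testing for a total of 3 ECPs included for this testing method".
- **Reproducibility.** "LFR-260 testing will be reproduced by two separate ECP operators at each location for a total of 6 ECPs". The steps are "ECP #1 will complete Refraction with LFR-260", then "ECP #1 will leave the room, and ECP #2 will complete Refraction with LFR-260". No interval is given. Assignment to Group I or II only places this pair of readings before or after the phoropter examination.

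Section 4.8 randomises, in blocks within site, which device is used first. It does not mention ECP order. Section 4.9.2 does not say whether ECP #1 is the same person for every subject at a location or a label for whoever goes first. The flowchart's reference to a second ECP does not settle this.

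For analysis, Section 7.7.4 says: "Reliability of LFR-260 will be conducted in a subset of subjects for which measurements will be obtained twice in an office context". It plans intraclass correlations (ICCs) without an operator, order or interval term, and describes in detail only the 33 subjects measured again at about 60 minutes. The Synopsis names repeatability and reproducibility together, also under ICCs. Section 2.3 says that precision testing is to confirm both properties.

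**The concern.** A reproducibility study with two operators is informative when the operator is the thing that changes between readings. Here the second reading always carries the label ECP #2, so any consistent shift from first to second reading (fatigue, learning, relaxation of accommodation) can enter the ECP contrast, and nothing in the plan keeps it out.

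The natural benchmark, the same-ECP pair, differs from the two-ECP pair in more than the operator: it spans about an hour, and it comes from different subjects. If initial testing in Section 4.9.2 means both devices, Group I repeatability subjects also have a phoropter examination between their two LFR-260 readings, and reproducibility subjects do not.

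At stake is what the trial can say about the precision statement in Section 2.3. An ECP difference might be an order effect, and an absent one might be two effects cancelling.

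**Working it through.** **The plan's own figure.** The documents give no size or precision calculation for either precision subset. The only calculation is primary power (Section 7.5): 216 eyes, 0.80 against 0.90, 1-sided exact binomial at 0.05. The smallest passing count is 183 of 216, with exact alpha 0.0461 and power 99.46%, so the stated 99% reproduces. It does not depend on the point below.

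**Step 1: what the mean differences can identify.** For each subject take second minus first LFR-260 reading. Let o be the order effect, t the additional effect of the one-hour interval, and d_k the difference between the two ECPs at location k (k = 1, 2, 3).

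| Design | Expected mean differences | Identifiable |
|---|---|---|
| Reproducibility alone, ECP #1 a fixed person | o + d_1, o + d_2, o + d_3 | 3 of 4 parameters |
| Both subsets, ECP #1 a fixed person | the above, and o + t | 4 of 5 |
| Reproducibility alone, order counterbalanced | o + d_k and o − d_k at each k | 4 of 4 |
| Both subsets, order counterbalanced | the above, and o + t | 5 of 5 |
| Both subsets, equal interval, fixed order | o, and o + d_k | 4 of 4, but only by comparing different subjects |

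With fixed roles, adding the repeatability subset adds one equation and one unknown. Operator and order then separate only if t is assumed to be zero. With both orders present, half the sum of the two means gives o and half their difference gives d_k.

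**Step 2: precision after counterbalancing.** With 6 and 5 of the 11 subjects per location in each order, and one difference per subject, the standard error is 0.30 × SD for one location's d_k and 0.17 × SD for o, where SD is that of the within-subject difference. As a check for one location alone: 0.5 × √(1/6 + 1/5) = 0.30.

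**Step 3: illustration of an order shift.** The documents give no shift; 0.12 D is assumed. With fixed order, all 0.12 D appears as an ECP difference. With a 6/5 split and no order term, 0.12 × (6 − 5)/11 = 0.011 D remains. With an order term, none remains in expectation.

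**Step 4: illustration of the interval mismatch.** Let s_e be the reading error SD, s_ECP the operator SD and s_time the SD of change over the hour, with no such change assumed in the two-ECP pair.

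- Same-ECP pair: V_same = 2s_e² + s_time²
- Two-ECP pair: V_two = 2s_e² + 2s_ECP²
- Operator variance by subtraction: (V_two − V_same)/2 = s_ECP² − s_time²/2

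All SDs below are assumed, because the documents give none.

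| s_ECP (D) | True s_ECP² (D²) | s_time 0.10 D | s_time 0.20 D | s_time 0.25 D |
|---|---|---|---|---|
| 0.10 | 0.0100 | 0.0050 | −0.0100 | −0.0212 |
| 0.15 | 0.0225 | 0.0175 | 0.0025 | −0.0088 |

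For example, 0.10² − 0.20²/2 = 0.0100 − 0.0200 = −0.0100.

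**Step 5: the planned statistic.** A constant shift of 0.12 D adds 0.12²/2 = 0.0072 D² to the within-eye variance of a one-way ICC. With assumed s_e = 0.15 D (variance 0.0225) and a between-eye sphere SD of 1 D, the ICC moves from 1/1.0225 = 0.978 to 1/1.0297 = 0.971. With an SD of 2 D it moves from 4/4.0225 = 0.994 to 4/4.0297 = 0.993, a fall of 0.002 before rounding. Section 7.7.4 does not name the ICC form: an absolute-agreement ICC counts such a shift and a consistency ICC ignores it.

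**The case against.** **ECP #1 may be only a label.** A reader might infer that one person always goes first, so that operator and order can never be separated. The protocol does not say so. If the two ECPs swap roles within each location, all parameters are estimable. This stands, and it makes the full confounding conditional. It does not remove the point, because nothing requires the roles to rotate. Likewise, that the two readings are consecutive is a fair inference from the steps, not a stated interval.

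**The plan never subtracts repeatability from reproducibility.** Correct. It plans ICCs, so a reader should not infer that the trial would report a wrong or negative operator variance. The figures in Step 4 only show why the two subsets are not comparable. Nor do the documents say that the two kinds of pair will be pooled; Section 7.7.4 is simply silent on the two-ECP subset.

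**The effect on the ICC is small.** For sphere, under the assumptions of Step 5, it is. But an ICC that barely moves for an order shift barely moves for an operator bias of the same size, so this says little about reproducibility.

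**The repeatability subset offers a control.** It is also a first-then-second reading with the operator held constant, so it gives a combined order-plus-time shift. This partly stands, but the combination can be unpicked only by assuming that the hour has no effect.

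**A subtracted operator variance would be imprecise even with equal intervals.** True. With 32 degrees of freedom per subset and s_ECP = 0.10 D, the standard error is 0.5 × √[(2/32)(V_same² + V_two²)]. That is 0.006 D² at s_e = 0.10 D (V = 0.02 and 0.04) and 0.016 D² at s_e = 0.20 D (V = 0.08 and 0.10), against a true 0.010. The remedy should therefore rest on counterbalancing and an order term.

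**Three ECPs for repeatability and six for reproducibility.** This is an explicit choice in Section 4.9.2, not an error.

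**Conclusion.** The point holds as a design weakness in the precision testing. No counterbalancing of ECP order and no interval is specified for the two-ECP readings, and no analysis term would separate the effects.

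If ECP #1 is a fixed person at each location, operator and order are fully confounded within the reproducibility subset (3 of 4 parameters identifiable; 33 subjects, 66 eyes). If the roles happen to rotate, they can be separated, but the protocol does not ensure it. On either reading the differing intervals prevent a difference between the two subsets (66 subjects, 132 eyes) from being attributed to the operator alone.

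The size in dioptres is unknown. The documents supply no operator, time or order SD, the numerical illustrations rest on assumed values, and no direction of bias is shown to be likely. No hypothesis or acceptance criterion attaches to precision, and the primary test and its power are untouched. It is worth changing because the change is cheap and because, if ECP #1 is fixed, analysis cannot recover the lost separation without assuming that the interval has no effect.

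**What to change.** In Section 4.9.2, item 2:

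- Say whether ECP #1 is a fixed person or a position in the sequence.
- Randomise or alternate within each location which of the two ECPs refracts first, for example 6 and 5 of the 11 subjects.
- Record ECP identity and order for each reading on the case report form.
- State the interval between the two readings, and match it to the repeatability subset if practical.

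In Section 7.7.4:

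- Analyse the same-ECP and two-ECP subsets separately.
- Include operator and order terms in the two-ECP analysis.

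Spreading the 11 repeatability subjects per location over both ECPs is optional.

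The cost is protocol wording and a short allocation list, with the same subjects, ECPs and number of refractions. If one hour is used in both subsets, 33 subjects wait longer. The ECP-order changes need to be in place before the reproducibility subset is enrolled.
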